## 2.5.2 Statistical hypothesis, model, and method of analysis

### Safety evaluation part

As the final analysis for the part 1, all adverse events of all patients enrolled in the part 1 will be listed.

The Independent Safety Committee will review all available safety data in patients from Japan up to the time of the safety review data cut-off date. After determining whether each death or serious adverse event leading to treatment discontinuation during the safety evaluation period meets criteria for a Safety Event, it will consider this tabulation in combination with the entire safety experience in Japanese patients to determine the ongoing conduct of the trial.

### Randomized part

The primary efficacy analysis for the part 2 will be the comparison of the distribution of EFS between the two treatment arms. The estimated hazard ratio (HR) of EFS not censored at SCT will be calculated using Cox regression model stratified according to the 2 stratification factors (FLT3 mutation status: ITD allelic ratio < 0.7, ITD allelic ratio  $\geq$  0.7, TKD; and regimen: RATIFY regimen, JALSG regimen) as per IRT (or CRF as this is the same as IRT considering a subject with both ITD allelic ratio < 0.7 and TKD as that with ITD allelic ratio < 0.7). In addition, associated 95% Wald confidence interval (CI) will be calculated. The success of the study will be claimed when estimated HR is less than 1. (Note: The success criteria of the study was judged at interim and/or primary analysis and not at this final analysis.)

The survival distribution of EFS will be estimated using the Kaplan-Meier method. The results will be plotted graphically by treatment arm. The median of EFS along with 95% CIs will be presented by treatment arm.

### 2.5.3 Handling of missing values/censoring/discontinuations

In the final analysis for the part 2, EFS will be censored at the date of the last adequate clinical assessment if no EFS event is observed prior to the LPLV.

The date of last adequate clinical assessment will be the final timepoint for the evaluation of efficacy before an event or a censoring reason occurred. In this case the last clinical assessment date at that assessment will be used. If no post-baseline assessment is available and the patient is still on treatment at the time of the analysis, then the date of randomization will be used and EFS censored.

Refer to [Table 2-4](#) for censoring and event date options and outcomes for EFS.

**Table 2-4      Outcome and event/censor dates for EFS analysis**

Situation	Date	Outcome
No baseline assessment	Date of randomization	Censored
No post-baseline assessment	Date of randomization	Censored
Treatment failure	Date of randomization + 1	EFS event
Relapse or death at or before next scheduled assessment	Date of relapse or death	EFS event
Relapse or death after exactly one missing assessment	Date of relapse or death	EFS event
Relapse or death after two or more missing assessments	Date of last adequate assessment prior to missed assessment	Censored
No relapse or death	Date of last adequate assessment	Censored
Strong CYP3A4 inducer given prior to protocol defined progression	Date of last adequate assessment	Censored
New anticancer therapy given prior to protocol defined relapse	Ignore the new anticancer therapy and follow situations above	As per above situations

### 2.5.4      Supportive analyses

#### Sensitivity analyses

The efficacy analysis for EFS will be repeated using the PPS if the number of patients in the FAS and PPS differ by more than 10 percent.

Further sensitivity analyses in the FAS will be performed for EFS per local review where:

- A sensitivity analysis by using EFS defined as the time from the start of the study treatment until an EFS event is observed.

- A sensitivity analysis considering SCT: patients are considered as censored at the time of the transplant if they received SCT.

In addition, the Bayesian posterior probability of (HR for EFS per local review < 1) will be calculated as a supportive analysis. Assuming a weakly informative prior distribution derived from Study [A2301] data, the distribution of the HR will be updated with all available data from the patients included in the FAS (for more detail, refer to [\[study protocol Section 14.1\]](#)).

If 36 EFS events are not documented at the time of final analysis, the Bayesian predictive probability of (HR for EFS when 36 EFS events are documented < 1) will be calculated. To calculate the predictive probability, assuming a weakly informative prior distribution derived from Study [A2301], data and the prior distribution will be updated using the available data from patients in the FAS at the time of analysis (for more details of weakly informative prior, refer to [\[study protocol Section 14.1\]](#)).

## **Subgroup analyses**

Subgroup analyses specified in [Section 2.2.1](#) to assess the homogeneity of the treatment effect across demographic and baseline disease characteristics will be performed.

For each of the subgroups, the treatment effect will be assessed separately within each category. The HR and their 95% CIs will be presented by means of forest plots. Forest plot for EFS will be conducted by unstratified analysis for each subgroup because this study is small sample size study and it is difficult to conduct stratified analysis for each subgroup.

## **Censoring pattern of EFS**

Number of patients with a EFS event and number of patients censored for the EFS analysis will be summarized. In addition, a summary of reasons for EFS censoring will be provided by treatment arm based on the following reasons:

1. Ongoing without event
2. Lost to follow-up
3. Withdrew consent
4. Adequate assessment no longer available
5. Event after  $\geq 2$  missing efficacy assessments

The EFS censoring reasons are defined in the following way.

If the time interval between the last adequate date of the efficacy assessment and the earliest of the following dates is smaller or equal to interval of 2 missing efficacy assessments :

1. Analysis cut-off date (i.e., LPLV),
2. Date of consent withdrawal,
3. Visit date of study treatment discontinuation or end of post-treatment follow-up discontinuation due to lost to follow-up.

Then the EFS censoring reason will be:

1. 'Ongoing',
2. 'Withdrew consent',

3. 'Lost to follow-up'.

If the time interval is larger than the interval of 2 missing efficacy assessments with no event observed, then the EFS censoring reason will always default to 'Adequate assessment no longer available'. If the time interval between the last adequate efficacy assessment date and the EFS event date is larger than the interval of 2 missing efficacy assessments then the patient will be censored and the censoring reason will be 'Event documented after two or more missing efficacy assessments'.

## **2.6 Analysis of the key secondary objective**

Not applicable.

## **2.7 Analysis of secondary efficacy objective(s)**

The secondary objectives in this study are:

- To determine overall survival (OS) in the two treatment groups
- To determine the rate of complete remission (CR) in the two treatment groups
- To determine the cumulative incidence of relapse (CIR) in the two treatment groups
- To evaluate the safety of midostaurin compared to placebo in combination with chemotherapy and as single agent continuation therapy
- To evaluate the pharmacokinetics of midostaurin and its two major metabolites CGP52421 and CGP62221
- To determine the effect of the study treatment on quality of life

### **2.7.1 Secondary endpoints**

#### **Overall survival (OS)**

OS is defined as the time from the date of randomization to date of death due to any cause. All deaths occurring on or before the LPLV in the FAS will be used in the OS analysis. If a patient is not known to have died at the time of LPLV, OS will be censored at the date of last contact.

#### **Complete remission (CR) rate**

CR rate is defined as the proportion of patients with a CR according to Cheson criteria (Cheson 2003) as per investigator assessment. CR rate will be calculated using the FAS.

#### **Cumulative incidence of relapse (CIR)**

Cumulative incidence of relapse (CIR) is defined for patients who have achieved CR only. CIR will be calculated from the date of first CR to relapse or death due to AML, whichever occurs first. If a patient is not known to have relapse at the time of LPLV, CIR will be censored at the

date of last adequate assessment. If a patient has died due to other reason than AML without relapse prior to death, CIR will be censored at the date of the death.

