Initial therapy for AML in younger patients (generally less than 60 years of age) has a goal of inducing a durable complete remission and has changed little in the past three decades. For patients with an adequate performance status, initial therapy comprises the “7 + 3” remission induction regimen with daunorubicin and cytarabine, followed by high dose cytarabine for remission consolidation. The 5-year survival rate with this approach is 30 to 40% in patients under the age of 60 years, and the rate is less than 15% in older patients (Stone et al 2005). Patients with AML characterized by poor prognostic features are recommended to enroll into clinical trials and/or to undergo stem cell transplantation (SCT) following achievement of remission with standard induction chemotherapy (Schiller 2014). Significant improvements in OS and DFS for AML patients harboring FLT3-ITD mutations have been reported with allo-SCT compared to chemotherapy alone or autologous SCT (DeZern et al 2011, Brunet et al 2013), especially for patients with high FLT3-ITD allelic ratios (Schlenk et al 2014). However, these patients remain at high risk of relapse following SCT compared to patients without FLT3-ITD mutations, with a higher 2-year relapse incidence (30% vs 16%; p=0.006) and lower leukemia free survival (58% vs 71%; p=0.04) (Brunet et al 2012). Not all patients are eligible for transplantation, particularly those of advanced age. SCT is associated with a substantial risk of treatment-related complications and post-transplant relapses, particularly in leukemias with high risk features such as the FLT3-ITD mutation with a high allelic ratio. Thus, despite the availability of SCT therapy for some patients, there remains a high unmet medical need in FLT3-mutated AML.

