**Table 1-1 Objectives and related endpoints**

Objective	Endpoint	Analysis
Primary		
Safety Evaluation part (Part 1, Japan only)		
To Evaluate the safety and tolerability of midostaurin in combination with daunorubicin/cytarabine induction and high-dose cytarabine consolidation in Japanese patients with newly diagnosed AML.	Incidence and severity of Safety Events, defined as death or serious adverse event leading to treatment discontinuation that occurs on or before Day 21 of the first Consolidation cycle and that is determined by the Independent Safety Committee to be definitely or probably related to midostaurin.	
Double-blind, randomized, placebo-controlled (Part 2)		
To Evaluate the efficacy based on event-free survival (EFS) of midostaurin versus placebo in combination with daunorubicin/cytarabine induction, with high-dose cytarabine consolidation, and with midostaurin single agent continuation therapy in newly diagnosed patients with FLT3-mutated AML.	Event-free survival (EFS) defined as the time from the date of randomization until an EFS event is observed. An EFS event is defined as a failure to obtain a CR within induction 2, relapse after CR, or death due to any cause, whichever occurs first.	Section 2.5
Secondary		

Objective	Endpoint	Analysis
Randomized part (Part 2)		
Determine overall survival (OS) in the two treatment groups	Overall survival (OS), defined as the time from the date of randomization to date of death due to any cause.	Section 2.7
Determine rate of complete remission (CR) in the two treatment groups	CR rate, defined as the proportion of patients with a CR according to Cheson criteria, at various timepoints.	
Determine cumulative incidence of relapse (CIR) in the two treatment groups	CIR (only for patients who have achieved CR after study treatment initiation), as measured from the date of first CR to relapse or death due to AML, whichever occurs first.	
Evaluate safety of midostaurin compared to placebo in combination with chemotherapy and as single agent continuation therapy	Frequency/severity of AEs, ECG and laboratory abnormalities.	Section 2.8
Evaluate the pharmacokinetics of midostaurin and its two major metabolites CGP52421 and CGP62221	Pharmacokinetic parameters for midostaurin and two major metabolites CGP52421 and CGP62221.	Section 2.10

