### Cumulative incidence of relapse (CIR)

The survival distribution of CIR distributions will be estimated using the Kaplan-Meier method, and Kaplan-Meier curves, medians and 95% CIs ([Brookmeyer and Crowley 1982](#)) of the medians will be presented for each treatment arm. The HR for CIR will be calculated, along with its 95% CI, using a stratified Cox model using the randomization stratification factors.

As a sensitivity analysis, the same analyses when patients are considered as censored at the time of the transplant if they received SCT will be performed.

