## **4 Change to protocol specified analyses**

In section 2.11 (patient-reported outcomes), the primary PRO variables of interest of QLQ-C30 was changed from total score to the global health status/QoL score to revise to the correct variable.

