### **Kaplan-Meier estimates**

An estimate of the survival function in each treatment group will be constructed using Kaplan-Meier (product-limit) method as implemented in PROC LIFETEST with METHOD=KM option. The PROC LIFETEST statement will use the option CONFTYPE=LOGLOG.

Median survival for each treatment group will be obtained along with 95% confidence intervals calculated from PROC LIFETEST output using the method of [Brookmeyer and Crowley 1982](#). Kaplan-Meier estimates of the survival function with 95% confidence intervals at specific time points will be summarized. The standard error of the Kaplan-Meier estimate will be calculated using Greenwood's formula [Collett 1994](#).

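### The CIR curves and medians censor non-AML deaths in remission and use Kaplan-Meier, so they do not estimate a cumulative incidence of relapse

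*SAP*

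**What the plan says.** SAP Table 1-1 lists the objective: "Determine cumulative incidence of relapse (CIR) in the two treatment groups". SAP 2.7.1 restricts the endpoint to patients who reached CR and defines it: "CIR will be calculated from the date of first CR to relapse or death due to AML, whichever occurs first". The rule for other deaths is that where someone "died due to other reason than AML without relapse prior to death, CIR will be censored at the date of the death". Protocol 10.5.2.3 has the same rule.

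For estimation, SAP 2.7.2 states: "The survival distribution of CIR distributions will be estimated using the Kaplan-Meier method, and Kaplan-Meier curves, medians and 95% CIs". The medians are given by arm, with a hazard ratio from a Cox model stratified by the randomization factors. The only CIR sensitivity analysis adds censoring at stem cell transplantation (SCT).

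SAP 5.4.1 specifies only the Kaplan-Meier option of PROC LIFETEST and says: "Kaplan-Meier estimates of the survival function with 95% confidence intervals at specific time points will be summarized". Neither document mentions a cumulative incidence function, a competing event, a Gray test or a Fine-Gray model. SAP section 4 records a single departure from the protocol: "the primary PRO variables of interest of QLQ-C30 was changed from total score to the global health status/QoL score". The CIR method is therefore carried over unchanged from the protocol.

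**The concern.** Censoring is appropriate when the patient could still have the event after leaving observation. A patient who dies in remission of a non-AML cause cannot. Kaplan-Meier nevertheless treats that patient as if he or she had the same later relapse risk as those still followed. What it estimates is the relapse probability in a setting where non-AML death does not occur, and even that requires the two causes to be independent. It is not the proportion of CR patients who relapse, which is what the endpoint's name promises and how its curves and medians would be read.

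Non-AML deaths in remission are plausible here. Because censoring at SCT is only a sensitivity analysis, the main CIR analysis includes follow-up after transplant, and protocol 1.1 says: "SCT is associated with a substantial risk of treatment-related complications and post-transplant relapses". The excess also need not be equal in the two arms.

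**Working it through.** The documents give no CIR rate, so there is no planned figure to reproduce. The size of the effect can be illustrated from protocol Table 14-1 (study A2301 EFS).

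**Inputs**

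| | Midostaurin | Placebo |
|---|---|---|
| Patients, N | 360 | 357 |
| Treatment failures | 125 | 150 |
| Relapses, r | 98 | 102 |
| Deaths as first event, d | 21 | 25 |
| Assumed in CR (N minus failures) | 235 | 207 |

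The counts add up: 125 + 98 + 21 = 244, and 150 + 102 + 25 = 277, as in the table.

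**Assumptions.** All these deaths occurred in CR, follow-up has a common horizon, and the cause-specific hazards are proportional. The share f of deaths that are non-AML is not given, so the whole range from 0 to 1 is used.

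**Formulas.** Events of interest: e = r + (1 - f)d. All first events: F = (r + d)/CR, which is 119/235 = 0.506 and 127/207 = 0.614.

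- Cumulative incidence = e/CR
- 1-KM = 1 - (1 - F)^(e/(r + d))

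Worked for f = 1:

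- Midostaurin: 98/235 = 41.7%; 1 - (116/235)^(98/119) = 44.1%.
- Placebo: 102/207 = 49.3%; 1 - (80/207)^(102/127) = 53.4%.

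For f = 0.5, e = 108.5 and 114.5.

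| Non-AML share of deaths | Midostaurin: cumulative incidence / 1-KM | Excess (points) | Placebo: cumulative incidence / 1-KM | Excess (points) |
|---|---|---|---|---|
| None | 50.6% / 50.6% | 0 | 61.4% / 61.4% | 0 |
| Half | 46.2% / 47.5% | 1.3 | 55.3% / 57.6% | 2.2 |
| All | 41.7% / 44.1% | 2.4 | 49.3% / 53.4% | 4.1 |

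Excesses are taken from unrounded values. With all deaths non-AML, placebo reaches a Kaplan-Meier median although its cumulative incidence stays below 50%. The gap between arms grows from 49.3 - 41.7 = 7.6 points to 53.4 - 44.1 = 9.3 points, in midostaurin's favour.

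As a purely hypothetical stress case, doubling the non-AML death hazard relative to the last row leaves 1-KM unchanged but lowers the cumulative incidence to 39.5% and 45.6%. The excess is then 4.6 and 7.8 points.

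**At this trial's size.** With 62 patients randomized, or 31 per arm, about 31 × 235/360 = 20 and 31 × 207/357 = 18 would reach CR. I simulated 20,000 trials with exponential cause-specific hazards and a common horizon. When all deaths are non-AML, the mean number of such deaths is 1.8 and 2.2, and the mean excess is 2.4 and 4.1 points. Some excess appears in at least one arm in 97% of trials, and in about 83% when half the deaths are non-AML. It appears in both arms in about 70% and 35%. The standard deviation of the cumulative incidence itself is 11 to 12 points per arm.

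**The case against.** The strongest reply is that this matters little. CIR is one of several secondary endpoints with no alpha attached, and the only planned comparison between arms, the Cox hazard ratio, is valid as a cause-specific hazard ratio. An excess of 1 to 4 points is small beside sampling error of 11 to 12 points per arm. In the difference between arms the bias is at most 9.3 - 7.6 = 1.7 points in the A2301 range, against a sampling standard deviation of about 16. The simulated percentages count any excess, however small: with all deaths non-AML it is below 1 point in 30% of midostaurin arms and 18% of placebo arms. Table 14-1 gives neither the cause of death nor whether it followed CR, and the SCT statement in protocol 1.1 gives no non-relapse mortality figure.

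These points stand as limits on the size. They do not make the curve an estimate of what it is called. The error runs one way, and sampling noise and confidence intervals do not correct it.

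A second reply concerns timing. The SAP is dated December 2022, after the primary analysis and its planned unblinding. The Kaplan-Meier method is in the protocol, and the study is meant to be compared with A2301, whose CIR method the documents do not describe. This is a fair reason not to remove the planned output silently. It is met by keeping that output under a correct label and logging the addition. SAP section 4 already corrects one protocol-specified variable in this way.

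**Conclusion.** The concern holds. As written, the CIR curves, medians and time-point estimates do not estimate a cumulative incidence, and they can only err upward. The A2301 illustration puts the excess at 0 to 2.4 points on midostaurin and 0 to 4.1 on placebo. That range rests on the stated assumptions about CR numbers, timing of deaths, follow-up and hazards, and on the unknown non-AML share of deaths. The actual size will depend on how many patients in this trial die in remission of other causes. The problem should be fixed because a named efficacy endpoint would otherwise be misreported, but it does not touch the EFS success claim.

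**What to change.** In SAP 2.7.2:

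- Report the Aalen-Johansen cumulative incidence of relapse or AML death by arm, with non-AML death in CR as the competing event. Give it at fixed times (for example 12 and 24 months) with 95% confidence intervals. PROC LIFETEST with EVENTCODE does this.
- Drop the Kaplan-Meier median and curve, or keep them for continuity with the primary analysis and A2301 under a label saying that they are not a cumulative incidence.
- Keep the stratified Cox hazard ratio and label it cause-specific.
- In the SCT sensitivity analysis, keep censoring at transplant as planned, and treat non-AML death as the competing event there too.
- Record the change in SAP section 4.

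A Gray test or Fine-Gray model is optional in a study declared to be one of estimation. The cost is a few lines of SAP text, one entry in section 4 and standard SAS code. No new data are needed, because the planned censoring rule already requires cause of death.

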## 2.7.2 Statistical hypothesis, model, and method of analysis

### Overall survival (OS)

The OS distribution not censored at SCT will be estimated using the Kaplan-Meier method, and the Kaplan-Meier curves, medians and 95% CIs of the medians will be presented for each treatment arm. The HR along with its 95% CI will be calculated, using a stratified Cox model using the randomization stratification factors.

As sensitivity analyses performed in the FAS, the hazard ratio and 95% CI for OS will be obtained from:

- A sensitivity analysis by using OS defined as the time from the start of the study treatment until an OS event is observed.
- A sensitivity analysis considering SCT: patients are considered as censored at the time of the transplant if they received SCT.

Regardless of OS results, subgroup analyses specified in [Section 2.2.1](#) to assess the homogeneity of the treatment effect across demographic and baseline disease characteristics will be performed. Note: same analysis was conducted for primary CSR with changed from planned analysis at the time of primary analysis although original analysis plan was to conduct if overall OS HR was less than 1.

For each of the subgroups, the treatment effect will be assessed separately within each category. The HR and their 95% CIs will be presented by means of forest plots. Forest plot for OS will be conducted by unstratified analysis for each subgroup because this study is small sample size study and it is difficult to conduct stratified analysis for each subgroup.

